### 8.8.2 Pharmacodynamics

Serum samples for PD analysis will be collected at the visits indicated in the SoA ([Table 1](#) and [Table 2](#)). In case of need for prioritization of blood analysis (considering weight and health status of the patient), laboratory safety parameters and PK assessments will be prioritized over biomarkers exploratory parameters.

Pharmacodynamics assessments include the measurement of:

- Free IFN $\gamma$  levels prior to NI-0501 treatment start, and total IFN $\gamma$  (free IFN $\gamma$ +bound to NI-0501) during NI-0501 treatment. Samples for total IFN $\gamma$  measurements will be taken pre-dose on infusion visits, except for the first infusion when free IFN $\gamma$  will be measured pre-dose and total IFN $\gamma$  post-dose.
- Chemokines known to be induced by IFN $\gamma$  (CXCL9, CXCL10). On infusion visits, serum samples will be collected pre-dose only.
- Other potential disease biomarkers (e.g. sCD25, sCD163, IL-18, IL-10, IL-6, TNF $\alpha$ , CXCL11). Serum samples will be collected on SD0 and every 2 weeks during the course of the study.

In case of CNS involvement, if lumbar puncture is performed for diagnostic and/or therapeutic purposes, biomarker analysis in CSF samples may be performed.

Details on sample preparation and handling will be described in a separate laboratory manual.

### 8.8.3 Immunogenicity

Serum samples for the assessment of ADAs will be collected on SD0 (prior to NI-0501 infusion) and at the End of Study visit, and in case of suspected loss of activity of NI-0501 during the study. Details on sample preparation and handling will be described in a separate laboratory manual.

## 8.9 WITHDRAWAL VISIT

The same procedures described for the EoS Visit should be followed by the Investigator for any patient who is withdrawn prematurely from the study, as soon as possible after the decision to withdraw is made.

For patients who withdraw from the study as a result of their own decision or the decision of their parent/guardian, the Investigator should contact the patient (or parent/guardian) and ask them to attend a withdrawal visit as soon as possible and in any case within 30 days from termination.

Patients who are withdrawn due to a serious adverse event (SAE) should be followed-up until the resolution of the event or until the outcome of the event is known and stable.

## 8.10 UNPLANNED (UNSCHEDULED) VISITS

Unplanned visits may occur, should the patient need to be assessed or treated for any clinical condition that arises during the study. This may include the evaluation and follow-up of AEs, SAEs or laboratory tests. The assessments (as detailed in the SoA) should always be performed *at minimum*, but additional evaluations may be added according to the clinical judgment of the Investigator.

### 8.10.1 Unplanned Assessments

Additional samples to assess laboratory parameters and PK/PD may be required for safety reasons and/or for a better characterization of the PK/PD profile.

The number of additional samples taken will depend on the body weight and health status of the patient. Sampling schedule will be proposed by the Sponsor and discussed with the Investigator.

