**Table 2 – Schedule of assessment: Evaluation period - from SD28 to SD56 (End of Study)**

Assessments			SD35 1 st Week Follow-up	SD42 2 nd Week Follow-up	SD49 3 rd Week Follow-up	SD56  4 th Week Follow-up – EoS 	Unscheduled Visit (UV) 
Hospitalization		8.1					
Concomitant medication (including information on glucocorticoid tapering)		8.2	X	X	X	X	
Clinical assessments	- Vital signs	8.3.1	X	X	X	X	X
	- Physical examination	8.3.2	X	X	X	X	X
	- MAS clinical signs and symptoms 	8.3.3	X	X	X	X	
Laboratory assessments	- CBC	8.4	X	X	X	X	
	- Lymphocyte subset	8.4				X	
	- Coagulation (aPTT, PT, D-Dimers, Fibrinogen)	8.4	X	X	X	X	
	- Biochemistry	8.4	X	X	X	X	
	- Serum pregnancy test	8.4				X	
	- Urinalysis	8.4				X	
Search for infections	- Mycobacterium Tuberculosis	8.5		X		X	
	- EBV, CMV, Adenoviruses	8.5		X		X	
Procedure	- ECG	8.7.1				X	
Imaging	- Abdominal US	8.6.1		X		X	
	- Chest X-ray	8.6.2				X	
	- Brain MRI 	8.6.3				X	
Histopathology	- CSF analysis (if coagulation allows) 	8.7.2				X	
PK	- emapalumab serum concentration	8.8.1	X	X	X	X	
PD 1	- IFN $\gamma$ , CXCL9, CXCL10, sCD25	8.8.2	X	X	X	X	
PD 2	- Other markers	8.8.2		X		X	
Immunogenicity (ADA)		8.8.3				X	

 If Emapalumab treatment needs to be prolonged beyond 4 weeks, additional weekly visits must be scheduled as appropriate in order to complete the required short-term 4-week follow-up.

 The same procedures described for End of Study Visit should be followed for any patient who is withdrawn prematurely from the study (see protocol [Section 8.9](#))

 Unscheduled Visit: depending on the reason for UV, additional assessments may be added according to the Investigator's clinical judgment (see protocol [Section 8.10](#)).

 Hospitalization: please note that the patients can be discharged from SD15 if their conditions allow, provided that there is no active infections requiring i.v. antimicrobial therapy.

 Brain MRI & CSF analysis: to be performed in case of neurological symptoms occurrence, whenever possible. If brain MRI and CSF analysis were done at screening, an End of Study exam should be performed, whenever possible.

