#### 8.10.1 Unplanned Assessments

Additional samples to assess laboratory parameters and PK/PD may be required for safety reasons and/or for a better characterization of the PK/PD profile.

The number of additional samples taken will depend on the body weight and health status of the patient. Sampling schedule will be proposed by the Sponsor and discussed with the Investigator.

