## 3.2. Sample Size

The sample size was not formally calculated. The sample size of approximately 12 evaluable patients (a minimum of 10 sJIA patients) is based on pragmatic considerations, and on the experience acquired from patients with primary HLH treated with emapalumab.

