## 6.1.5. Analysis Visit Windows

Statistical analyses will be based on scheduled visits as collected in the case report form (CRF) realigned on study days, which are defined based on the date of first emapalumab infusion (SD0) as follows:

Study Day = date of interest - date of first emapalumab infusion.

The following rules will be applied for MAS remission and glucocorticoid tapering.

- For the assessment of MAS remission and glucocorticoid tapering at Week 8, the SD56±5 days analysis period will be considered. Where several such observations occur in this time window, the one closest to SD56 will be selected. If there are 2 such observations that are equidistant from SD56, the observation that is after SD56 will be selected.
- For the assessment of time to MAS remission, see Section 6.1.7.

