## 9.2. Clinical Laboratory Evaluations

The number of patients with clinical laboratory values below, within, or above the normal range by time point and in relation to baseline will be tabulated for each clinical laboratory analyte (shift table). Denominator of the percentages will be the number of patients in the All Treated Population.

Clinical chemistry and hematology results will be presented in separate tables.

Urinalysis results will not be tabulated. Abnormalities in urinalysis results assessed as medically relevant will be recorded as AEs and analyzed as described in Section 9.1.

Pregnancy test results will be tabulated by visit.

All laboratory values will be displayed in the data listings and those that are outside the normal range will be flagged, along with corresponding normal ranges.

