# **Summary of Amended Sections**

SAP Section(s)/ Purpose	Initial text from SAP version 2.0	Rationale / Updated text
Section 6.1.5 – Analysis Visit Windows / Assessment selection	No rules specified for the selection of assessments where multiple assessments may be eligible for tables except for Week 8 assessment.	Rules for selection of assessments used in Week 8 assessment of MAS remission provided in section 6.1.5, however no information provided for other safety and efficacy analysis and timepoint.  /  "In case there are two (or more) assessments from a subject within
		the visit window, the assessment with the date closest to the expected visit date will be used for the efficacy and safety analysis. In the event that two assessments are available and equidistant from the expected visit date, the result from earliest assessment will be used. If there are still two or more assessments recorded during the same day, the earliest measurement before the emapalumab infusion will be used (not applicable for the assessment of MAS remission at Week 8). If there is no treatment on the selected day, the earliest assessment of the selected day will be selected (not applicable for the
		assessment of MAS remission at Week 8). If there is no possibility to identify the earliest assessment, the assessment with the earliest sequence number will be used."

AD-ST-33.06 Effective date: 12-Nov-2020

[figure not shown]
Version 2.0 | Date 22-Jul-2021 | AD-PR-109.02 Effective date: 17-Aug-2020 Page 5 of 18

SAP Section(s)/ Purpose	Initial text from SAP version 2.0	Rationale / Updated text
Section 6.1.7 - Derived variables/ New Age group variable	No age group was defined in the SAP version 2.0.	Results will be posted and published in Eudra CT and predefined age group should be displayed as per template, therefore age group variable will be created and presented in the demographic table.  /  The new age group variable will be defined as follows  Age Group Definition  Newborns (0- 0 \leq (Date of 27 days) informed consent - Date of Birth) \leq 27  Infant and 28 \leq (Date of toddlers (28 informed consent - days - 23 Date of Birth) and months) age in years = 1  Children (2- 2 <= age in years = 1  Children (2- 12 <= age in years <= 11 years) 11  Adolescents 12 <= age in years <= 17 years)
		From 18-64 18<= age in years years <= 64
		From 65-84 65 <= age in years years <= 84
		Over 85 85 <= age in years years

[figure not shown]

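### An abnormal result taken off schedule can miss every laboratory and vital-sign summary table, and the marked-abnormality summaries promised in the protocol are not in the SAP

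*Protocol*

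**What the plan says.** **Extra sampling.** Protocol 8.10 allows unplanned visits when a clinical condition needs assessment or treatment: "This may include the evaluation and follow-up of AEs, SAEs or laboratory tests". Section 8.10.1 goes further: "Additional samples to assess laboratory parameters and PK/PD may be required for safety reasons and/or for a better characterization of the PK/PD profile". At an unscheduled visit, protocol Table 2 fixes only vital signs and physical examination; beyond that, "depending on the reason for UV, additional assessments may be added".

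**Which values are analysed.** SAP 6.1.5: "Statistical analyses will be based on scheduled visits as collected in the case report form (CRF) realigned on study days". The errata to 6.1.5 cover several values in one window: "the assessment with the date closest to the expected visit date will be used for the efficacy and safety analysis". Ties go to the earlier value. For repeats on one day, the earliest is kept, and on infusion days the earliest taken before the infusion.

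**What is tabulated.** SAP 9.2 plans one shift table per analyte, with the All Treated Population as denominator; its description begins "The number of patients with clinical laboratory values below, within, or above the normal range by time point and in relation to baseline will be". In SAP 14.1 the only laboratory tables are these shift tables (chemistry and hematology) and pregnancy tests. SAP 9.3 summarises vital signs by study day and time point, taking the highest daily value for temperature. Neither the SAP, the errata nor the post-hoc analysis plan contains a worst post-baseline table.

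**What was promised.** Protocol 12.3.2 commits to marked-abnormality summaries, besides shift tables, for every laboratory test. SAP Section 11 does not list their removal and says that nothing else departs from the protocol.

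**The concern.** The evolution of blood counts, liver tests, ferritin, CRP and coagulation is a named safety endpoint (protocol 7.3, SAP 2.2.1). The natural safety question is how many patients ever had a markedly abnormal value. No planned laboratory table answers it.

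The selection rules also ignore severity. A sample taken because a patient is deteriorating is the one most likely to fall between planned days. If it shares a window with a routine sample, distance from the planned day decides which is used. A reader relying on the summary tables could therefore see a calmer laboratory picture than the data contain.

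**Working it through.** The plan gives no calculated figure to reproduce here (SAP 3.2: "The sample size was not formally calculated"). The check is a count of scheduled laboratory days, followed by an illustration.

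**1. Visits from SD6 to SD28.** Protocol Appendix D gives blood volumes per visit and per period. Let *k* be the number of visits from SD6 to SD28, two of which carry the larger volume.

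- Laboratory subtotal, treatment period: 6.5 + 5 × 4 + (*k* − 2) × 4 + 2 × 4.5. With *k* = 8 this is 59.5, the stated figure. With *k* = 7 it is 55.5, and with *k* = 9 it is 63.5.
- Total, treatment period: 59.5 + 3 + (3.5 + 1.5 + 1.5 + 2 + 1.5) + 6 × 2 + 2 × 3 = 90.5, as stated.
- Evaluation period: 4 + 4.5 + 4 + 5 = 17.5, and 17.5 + 1.5 + 2.5 + 1.5 + 3 = 26.0, both as stated.

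So *k* = 8, which agrees with the 10 infusions in the Appendix D footnote (SD0, SD3 and eight more).

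**2. Scheduled post-baseline laboratory days.**

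- SD1, 2, 3 and 5: 4
- SD6 to SD28: 8
- SD35, 42, 49 and 56: 4
- Total: 16 of 56 days (29%), that is 12 of 28 (43%) up to SD28 and 4 of 28 (14%) afterwards

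**3. Illustration: how often a short abnormality touches no scheduled day.** My assumptions: it lasts *L* days, onset is uniform, visits fall on the planned day, and off-schedule values are not used. After SD28 there are four gaps of six unscheduled days. Each gap holds 7 − *L* onsets that miss every visit, out of 29 − *L* possible onsets in the 28 days:

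share missed = 4(7 − *L*) / (29 − *L*)

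| *L* (days) | SD29–56 | SD1–56 |
|---|---|---|
| 1 | 24/28 = 86% | 71% |
| 2 | 20/27 = 74% | 51% |
| 3 | 16/26 = 62% | 32–33% |
| 5 | 8/24 = 33% | 15% |
| 7 | 0% | 0% |

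The SD1–56 column enumerates all onsets, with the twice-weekly days taken as SD19/22/26/28 or SD18/22/25/28. An abnormality lasting a week is always caught.

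**4. Weight of one patient.** 1/12 = 8.3 percentage points.

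**5. Direction.** The worst of all values is never milder than the worst of a subset. An ever-abnormal count read from selected values can therefore equal the full count or fall below it, but not exceed it.

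**The case against.** - **Exclusion is implied, not stated.** A reader might infer that unscheduled values are dropped outright. No sentence says so. The errata choose among the assessments in a window without restricting them to scheduled ones, so an unscheduled value nearer the planned day could be selected. Windows for the safety tables are not defined; the ±3-day and SD56 ±5-day windows belong to efficacy derivations. This stands, and it leaves a rule that needs stating. Either way, severity plays no part in which value is kept.
- **The values are not lost.** All laboratory and vital-sign results are listed; out-of-range laboratory values and systolic falls of 30% or more are flagged. SAP 12.1 plots CRP, ferritin, triglycerides, ALT, AST, LDH, WBC, platelets and D-dimer per patient by study day. With about 12 patients that is a fair display. It gives no counts, and the list omits hemoglobin, neutrophils, bilirubin, creatinine, fibrinogen, PT and aPTT, although tests may be added.
- **Adverse event tables catch part of it.** Under protocol 10.3.1, abnormalities needing specific treatment are adverse events, and findings that indicate MAS worsening are reported as that event. This covers much of the deteriorating-patient case. It does not count the analyte, and it leaves out untreated abnormalities unrelated to MAS.
- **Extra samples need not be bad news.** Some serve PK/PD characterization or show recovery. The by-visit distributions therefore have no certain direction of bias; only the ever-abnormal reading does.
- **Temperature** already uses the daily highest value, so that part of the vital-sign concern falls away.

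**Conclusion.** The point holds as a gap in the safety summaries. An off-schedule or same-window worse value can be absent from every laboratory and vital-sign summary table, and an analysis promised in protocol 12.3.2 is missing without being declared. It invalidates no endpoint.

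The firm figures are the scheduled coverage (16 of 56 days, and 4 of 28 after SD28) and 8.3 points per patient at N = 12. The shares missed rest on the assumed durations and uniform onset. How many abnormal values will be taken off schedule is unknown.

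A reader might turn this into a specific misreport, such as 0/12 (exact 95% CI 0 to 26.5%) in place of 3/12 (5.5 to 57.2%). The documents do not support that: the shift tables have no ever-abnormal row, no intervals are specified for them, and the 3 would be invented. For ferritin a zero count is also implausible, because eligibility requires a value above 684 ng/mL.

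**What to change.** Keep the by-visit tables, and make three changes:

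1. **SAP 9.2:** add, per analyte, a shift table of baseline against worst post-baseline value (lowest and highest), or a marked-abnormality table. Use all scheduled and unscheduled results through end of study, with patients having any post-baseline value as denominator.
2. **SAP 9.3:** do the same for blood pressure, heart rate and oxygen saturation.
3. **SAP 6.1.5:** say how unscheduled values enter the by-visit tables, and that the scheduled-visit and nearest-value rules do not apply to the worst-value tables.

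If the marked-abnormality summaries are still to be left out, Section 11 should declare it. If the database is already locked, SAP Section 1 allows the new tables as post-hoc analyses labelled as such in the study report.

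The cost is a short SAP addition and one or two tables from data already collected. The safety figures may look slightly less favorable.

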## 9 STUDY SCIENTIFIC OVERSIGHT

A Scientific Steering Committee (SSC) composed of international experts in pediatric rheumatology as well as in HLH has been involved in the preparation of study design and protocol writing.

The SSC is also to be consulted for the composition of the independent Data Monitoring Committee (iDMC).

The SSC will continue to play an advisory role throughout the course of the study, including the support to the iDMC oversight, and will perform evaluations of the data to support the Sponsor in the interpretation of the results of the study.

Please refer to [Appendix C](#) for full details of membership of the SSC.

## 10 SAFETY MONITORING

### 10.1 INDEPENDENT DATA MONITORING COMMITTEE

The iDMC, composed of relevant experts (pediatric rheumatologist, pediatric onco-hematologist with experience in HLH, pediatric immunodeficiency/infectious disease specialist, bio-statistician and a specialist in ethics), will oversee the study, with particular regard to the evaluation of safety parameters and benefit/risk profile of NI-0501, reviewing all data generated on an ongoing basis with the aim to ensure that patients are not exposed to unnecessary risks. Some of the iDMC members have been already involved in the oversight of the ongoing NI-0501 studies. Please refer to [Section 10.5.1](#) for further details on the iDMC.

### 10.2 DESCRIPTION OF SAFETY PARAMETERS

Evaluation of NI-0501 tolerability and safety will be based on the following parameters:

- Adverse events (AEs), with special attention being paid to events temporally related to the infusion of NI-0501 (occurring during the infusions and within 24 hours post infusion) and to the occurrence of infections
- Laboratory parameters, as described in [Section 8.4](#)
- Vital signs, as described in [Section 8.3.1](#)

- Physical examination with particular attention paid to evolution of signs and symptoms present at baseline, and to any emergent new signs or symptoms (see [Section 8.3.2](#) for more details).

### 10.3 RECORDING AND REPORTING SAFETY PARAMETERS

#### 10.3.1 Adverse events

Adverse events (AEs) are defined as any undesirable experience occurring to a subject during the study, whether or not considered related to the IMP. All AEs reported spontaneously by the patients or his/her relatives or observed by the Investigator or his staff during the clinical study from the signature of the ICF up to and including the EoS visit will be reported on the AE data collection form.

Medical conditions present at screening (before ICF signature) should be recorded in the medical history section of the CRF.

All AEs will be reported in the appropriate section of the CRF.

An AE which occurs between start of screening visit (after ICF signature) and start of first IMP administration will be considered as a pre-treatment AE.

Any AE that occurs after the start of the first IMP administration will be considered in the study as Treatment Emergent Adverse Event (TEAE).

However, if a pre-existing medical condition recorded in the medical history worsens (clinically significant change in intensity or frequency), it must be recorded as an AE in the CRF and, depending on the time of its occurrence, will be considered as a pre-treatment AE or a TEAE. If a medical condition, recorded as a pre-treatment AE, worsens it will be recorded in the CRF as a separate TEAE.

For each AE, the following will be assessed and recorded: intensity, relationship to the IMP, action taken regarding the IMP, any treatment received for the event and outcome of AE to date.

Intensity of AEs will be graded on a three-points scale (mild, moderate, severe) using the modified WHO (World Health Organization) toxicity scale (Grade 3 and 4 are considered to be the severe grade). If AE severity cannot be assessed by this scale, assessment by the Investigator should be made using the following definitions:

- Mild: discomfort noticed but no disruption of normal activity,
- Moderate: discomfort sufficient to reduce or affect normal daily activity,
- Severe: inability to work or perform normal daily activity.

For a given AE, the assessment of its intensity should reflect the highest grade (on the 3 points scale mentioned above) reported during its course (except when the intensity of a pre-treatment AE increases after treatment initiation, as indicated above).

The relationship of the AE to the IMP will be assessed by the Investigator using a “Yes/No” classification. A “Yes” relationship infers that there is a reasonable possibility of causal relationship between the AE and IMP. The expression “reasonable possibility” is meant to convey that there are facts, evidence or arguments to suggest a causal relationship. Conversely, a “No” relationship infers that there is no reasonable possibility of causal relationship between the AE and IMP. Usually it implies that other possible causes have been identified.

In this study NI-0501 is the only IMP.

### 10.3.2 Serious Adverse Events

An adverse event is considered serious if it:

- results in death (note: death is an outcome, not an event);
- is life-threatening; (note: the term "life-threatening" refers to an event in which the patient was at immediate risk of death at the time of the event; it does not refer to an event which could hypothetically have caused a death had it been more severe);
- requires in-patient hospitalization or prolongs an existing hospitalization;
- results in persistent or significant disability/incapacity;
- is a congenital anomaly/birth defect;
- is an important medical event that may not result in death, be life-threatening, or require hospitalization but may be considered serious when, based upon appropriate medical judgment, they may jeopardize the patient and may require medical or surgical intervention to prevent one of the outcomes listed above. Examples of such medical events include allergic bronchospasm requiring intensive treatment in an emergency room or at home, blood dyscrasias or convulsions that do not result in inpatient hospitalization, or the development of drug dependency or drug abuse.

For the purposes of this study, the following will not be considered as serious adverse events:

- Elective hospitalizations or surgical procedures that are a result of a patient's pre-existing condition(s) which has (have) not worsened since receiving IMP. Such events should still be recorded as adverse events in the eCRF;
- Hospitalization as requested per protocol for NI-0501 infusion and study visits.

Any serious adverse event (SAE) that occurs during the course of the study, irrespective of the treatment received by the subject and regardless of causality to the study drug, must be communicated by the Investigator to NovImmune, by fax or electronic transmission, within 24 hours of awareness.

For the initial SAE report, the Investigator should report all available case details concerning the patient and the event, using the Novimmune SAE reporting standard form provided to the Investigators.

